### 3.4 Complications since implantation:

Type, seriousness, severity (intensity), relatedness (device alone; device and/or procedure), Clavien-Dindo classification, System Organ Classes, High Level Term according to MedDRA, treatment initiated and localization of pain concerning side effects occurred since implantation, date of event onset according to IUGA classification and chronicity will be described.

If a complication/adverse event is declared by a patient, a medical confirmation by the investigator or the Scientific Committee will be required to be considered.

### 3.5 Study exit/ Withdrawal:

Completion of the study as planned and primary reason in case of discontinuation will be described.

## **4. EFFICACY AND SAFETY VARIABLES:**

During the intermediate analysis, a Scientific Committee (SC) consisting of 3 experts has been consulted for reviewing the Statistics Analysis Plan and adjudicating all the safety events.

This Scientific Committee recommended modifications on the definition of treatment success without PGI-I “Little better” response deemed not relevant, and that includes Clavien-Dindo grade > 3 which is more relevant than the “severe” criterium often misinterpreted by the investigators.

Consequently, the analyses will be performed as defined in the protocol and as recommended by Scientific Committee.

### 4.1 Primary endpoint:

As defined in protocol:

Treatment success defined by PGI as a little, much better and very better improved and absence of serious or severe related Adverse Event one year after implantation.

Table 1: Definition of treatment success

Patient Global Improvement (PGI-I)	Safety	
	No severe or serious related adverse event reported	At least one severe or serious adverse event reported
Very much better	success	failure
Much better	success	failure
Little better	Success	failure
No change	failure	failure
Little worse	failure	failure
Much worse	failure	failure
Very much worse	failure	failure

As recommended and defined by Scientific Committee /SC:

- Treatment success defined by PGI as much better and very better improved and absence of any serious neither severe nor  $\geq$  grade 3 of Clavien-Dindo classification related Adverse Event one year after implantation.

4.2 Secondary endpoints:

As defined in protocol:

- ✓ Treatment success defined by PGI as a little, much better and very better improved and absence of serious or severe related Adverse Event at first follow-up visit, 2 years and 3 years after implantation.
- ✓ PGI as a little, much better and very better improved at first follow-up visit, 1 year, 2 years and 3 years after implantation.

As recommended and defined by Scientific Committee /SC:

- ✓ Treatment success defined by PGI as much better and very better improved and absence of any serious neither severe nor  $\geq$  grade 3 of Clavien-Dindo classification related Adverse Event at first follow-up visit, 2 years and 3 years after implantation.

- ✓ PGI as much better and very better improved at first follow-up visit, 1 year, 2 years and 3 years after implantation.
- ✓ Treatment success defined by PGI as much better and very better improved, and absence of serious related Adverse Event at first follow-up visit, 1 year, 2 years and 3 years after implantation.
- ✓ Treatment success defined by PGI as much better and very better improved, and absence of  $\geq$  Grade 3 Clavien-Dindo classification related Adverse Event at first follow-up visit, 1 year, 2 years and 3 years after implantation.
- ✓ PGI as much better and very better improved at first follow-up visit, 1 year, 2 years and 3 years after implantation.

Objective exams at baseline, first follow-up visit, one year, two years, three years after implantation:

- ✓ cough stress test,
- ✓ number of pads/day,
- ✓ post-void residual volume,
- ✓ maximum urinary flow rate,

Subjective exams at: baseline, first follow-up visit, 1 year, 2 years and 3 years after implantation:

- ✓ total I-QOL score and subscale scores (ALB/PSI/SE),
- ✓ Total PISQ-12 score, Q5 Q6 and Q7 PISQ-12,
- ✓ total ICIQ score,
- ✓ satisfaction (only at follow-up visit),
- ✓ recommendation to a friend (only at follow-up visit)
- ✓ activity (only at first follow-up visit)

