PROTOCOL

SU017

A 3 Years Naturalistic Cohort Survey Of Altis® Single Incision Sling System For Female Stress Urinary Incontinence

A post-marketing and multicenter prospective observational cohort study in subjects with female stress urinary incontinence

Date of edition: 26 June 2014

Final Version 1.2

This confidential document is the property of Coloplast Manufacturing France SAS
No unpublished information contained herein may be
disclosed without written approval of Coloplast.

> SYNOPSIS OF THE PROTOCOL

TITLE	
A 3 Years Naturalistic Cohort Survey Of Altis® Single Incision Sling System For Female Stress Urinary Incontinence
 
A post-marketing and multicenter prospective observational cohort study in subjects with female stress urinary incontinence

SPONSOR	
Coloplast Manufacturing France SAS. [name]

DEVICE	
Altis Single Incision Sling System

STUDY TYPE	
Post-market and prospective observational cohort study of subjects implanted with the Altis SIS for female stress urinary incontinence

OBJECTIVES	
Main study objective
 
To monitor the use of Altis Single Incision Sling in a real world population.
 
To assess the clinical effectiveness (defined by the treatment success rate) and to monitor safety of Altis SIS at 12 months post device implantation in women with stress urinary incontinence.
 
Success will be regarded as optimal if the PGI-I score is rated as very much or much or a little improved and no severe/serious event has been reported.
 
Secondary objectives.
 
To assess the clinical effectiveness of Altis SIS over the 3 years post device implantation follow up in real subject population
 
To explore pre-surgery prognosis factors of effectiveness and failure
 
To explore impact of Altis SIS on quality of life
 
To explore impact of Altis on sexual life
 
To document emergent device-related adverse events and safety over the 3 years post device implantation

POPULATION	
Target Subject Population
 
All subjects meeting selection criteria will be invited to participate in the registry. Participating sites are required to do their best efforts to document in the registry all enrolled subjects including those with early revision of the sling for any reason.

Inclusion criteria

1. Female gender
2. At least 18 years of age.

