## **1. MAIN OBJECTIVES OF STUDY AND STATISTICAL ANALYSIS:**

Coloplast's Altis Single Incision Sling (SLIS) System is a minimally invasive system intended for the treatment of female stress urinary incontinence (SUI) resulting from urethral hypermobility and/or intrinsic sphincter deficiency in women.

To meet the requirements of the AFNOR standard, an observational study has been organized to prospectively collect short and mid-term data in the treatment of the female SUI with Altis SIS in the real world. Indeed, observational studies are essential to understand real world use and compliance patterns, estimate effectiveness, and to adequately evaluate risk management programs.

The primary objective is assessment of clinical effectiveness defined by success that is a composite criterion including the patient global impression of improvement (PGI; very much better, much better, little better) and the absence of serious/severe related adverse event (AE), one year after implantation definition.

The secondary objectives of the study are:

- Clinical effectiveness of Altis SIS over the 3 years of follow-up
- Comparison between pre and post inclusion for other outcomes:
  - Objective: cough stress test, uro-flowmetry exams: post-void residual volume and peak urine flow rate, weights of urinary protection.
  - Subjective: number of pads used, exploration of impact of Altis SIS on quality of life via PGI-I, I-QOL or ICIQ-UI-SF questionnaires, patient's satisfaction, and exploration of impact of Altis SIS on sexual life via PISQ-12 questionnaire.
- Documentation of emergent device-related A.E. and safety over the 3 years post implantation
- To explore the pre-surgery prognosis factors associated of treatment success.

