### 9.2 Effectiveness Analysis:

#### I. Primary endpoint **at one year:**

- PGI as a little, much better and very better improved and absence of neither severe or serious related Adverse Event classification (as protocol).
- PGI as much better and very better improved, and absence of neither serious or severe or  $\geq$  Grade 3 Clavien-Dindo related Adverse Event (as SC recommendations)

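### The SAP labels a related-events-only primary endpoint as the protocol's definition, although the protocol synopsis counts any severe or serious event, and the two safety columns of Table 1 overlap

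*SAP*

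**What the plan says.** The Objectives part of the protocol synopsis treats the result as a success when PGI-I is in one of the three improved categories, ending with "a little improved and no severe/serious event has been reported". Relatedness is not mentioned there.

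The SAP limits the safety component to related events throughout its prose:

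- Section 1 (primary objective): "the absence of serious/severe related adverse event (AE), one year after implantation definition".
- Section 4.1, under the heading that attributes the definition to the protocol: "absence of serious or severe related Adverse Event one year after implantation". Section 4.2 uses the same restriction, under the same heading, for the other visits.
- Section 9.2 (primary endpoint): "absence of neither severe or serious related Adverse Event classification (as protocol". The protocol-labelled secondary endpoints in 9.2 follow suit.

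Table 1 in SAP 4.1 heads its success column "No severe or serious related adverse event reported" and its failure column "At least one severe or serious adverse event reported".

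SAP section 4 undertakes that "the analyses will be performed as defined in the protocol and as recommended by Scientific Committee". It describes two changes made on the Scientific Committee's advice: dropping the lowest improved PGI-I category and bringing in a Clavien-Dindo grade. A restriction to related events is not one of them.

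**The concern.** There are two separate defects, both in the primary endpoint.

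The first is a label that does not match its source. A result reported as the protocol's endpoint would follow a narrower event rule than the only protocol definition available, and the reader would not be told. The SAP plans no version of the composite that counts unrelated severe or serious events. The synopsis wording does not look like shorthand: one of its secondary objectives does qualify adverse events as device-related, so it uses the qualifier where it wants one.

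The second is that Table 1, which defines the endpoint, has columns that are not complements. Some women satisfy both headings, and the table gives no rule for choosing.

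The primary result is a single proportion with no comparator, so the definition of success sets the number directly. The direction is also fixed: ignoring unrelated events can turn failures into successes but never the reverse.

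**Working it through.** **Step 1. The definitions side by side**

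| Place | Severe or serious events that cause failure | Presented as |
|---|---|---|
| Protocol synopsis, Objectives | any | the protocol's own statement |
| SAP 1 | related only | primary objective |
| SAP 4.1 and 4.2, text | related only | protocol definition |
| SAP 4.1, Table 1, success column | related only | definition of success |
| SAP 4.1, Table 1, failure column | any | definition of success |
| SAP 9.2 | related only | protocol definition |

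**Step 2. Table 1 cell by cell**

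Cross the 7 PGI-I rows with 3 event states: no severe or serious event, unrelated only, at least one related. This gives 7 × 3 = 21 cells.

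- No event: only the success-column heading applies, so the outcome is clear in all 7 rows.
- At least one related event: only the failure-column heading applies, so the outcome is failure in all 7 rows.
- Unrelated only: both headings apply. For very much better, much better and little better, one column gives success and the other failure. For the other 4 rows, both give failure.

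So 3 of the 21 cells have contradictory outcomes and 18 are unambiguous.

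**Step 3. The plan's own figure**

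SAP 2.2 gives p = 0.89, d = 0.05 and n = z²p(1−p)/d². With z = 1.96:

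n = 3.8416 × 0.89 × 0.11 / 0.0025 = 150.4, which agrees with the stated 150.

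**Step 4. Illustration of size**

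Inputs from the documents: p = 0.89 (SAP 2.2), about 600 women included (SAP 2.2), 20% attrition (SAP 2.2), 95% intervals (SAP 8).

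Assumptions:

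- 89% is used as the related-only success rate. SAP 2.2 takes it from a result on PGI alone, without a safety component.
- 600 × 0.80 = 480 women are evaluable at 12 months.
- u, the share of related-only successes who have an unrelated severe or serious event by 12 months, runs from 1% to 10%. The documents give no value for u.

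Any-event success = 0.89 × (1 − u), and the shift = 0.89 × u.

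| u | Any-event success | Shift, points | Women reclassified, of 480 |
|---|---|---|---|
| 1% | 88.1% | 0.9 | 0.89 × 480 × 0.01 ≈ 4 |
| 2% | 87.2% | 1.8 | ≈ 9 |
| 5% | 84.55% | 4.45 | ≈ 21 |
| 10% | 80.1% | 8.9 | ≈ 43 |

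The 95% half-width at n = 480 is 1.96 × √(0.89 × 0.11 / 480) = 0.028, or 2.8 points. The shift reaches it at u = 0.028 / 0.89 ≈ 3.1%. The half-width is only a yardstick: the shift is a change of definition applied to the same women, and a larger sample would not reduce it.

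**The case against.** Several stronger readings are tempting, and the documents do not carry them.

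*The SAP contradicts the protocol as a whole.* The protocol text available is the synopsis. Its sentence is loose: it sits in an objectives paragraph, calls success optimal, and gives no attribution rule. A fuller endpoint section might specify related events, and the SAP's label might refer to that. This limits the claim to a mismatch with the synopsis. It does not remove the need to cite such a section and reconcile it.

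*Table 1 leaves the SAP's rule open, so programmers will obtain different primary results.* All SAP prose on the composite says related, and so does the success column. The failure heading has probably lost a word, and a programmer reading 4.1 and 9.2 together would most likely use related events. That makes Table 1 an editorial repair, but restoring the word leaves the mismatch with the synopsis untouched.

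*Every woman with an unrelated serious event is classified both ways.* This is true only in the three improved PGI-I rows.

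*The shift exceeds sampling error.* That needs u above about 3.1%, on assumed inputs. At 1% the shift is well inside the half-width. The SAP frames its safety data as complications and side effects, which could mean that few unrelated events are recorded.

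*The change was made to favour the device.* Nothing in the documents speaks to intent. Only the direction of the effect is established.

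It is also fair to say that no performance goal or threshold hangs on the rate. PGI-only success is reported at each follow-up visit, and the safety tables show relatedness. These outputs still do not allow a reader to reconstruct the any-event composite, because they do not join events to each woman's PGI-I response.

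**Conclusion.** The point holds as a mismatch between the SAP and the protocol synopsis, together with an inconsistent pair of headings in Table 1. The SAP's protocol-labelled primary endpoint is more lenient than, or at best equal to, the synopsis definition, and the SAP does not declare the difference.

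The effect on the success rate cannot be determined from the documents. The range of about 0.9 to 8.9 points is an illustration that rests on the assumed u, on 89% as the related-only rate and, for the comparison with 2.8 points, on 480 evaluable women.

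It should be fixed before the primary result is reported. It does not invalidate the study: the design is a descriptive single-arm cohort with a precision-based sample size, and no formal decision turns on the difference.

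**What to change.** 1. In SAP 4.1, 4.2 and 9.2, derive the protocol-labelled composite with any severe or serious event, citing the synopsis. Report the related-only composite beside it as a declared SAP modification, with the reason, and align the objective in SAP 1.
2. If a fuller protocol section specifies related events, cite it, reconcile it with the synopsis, and give the any-event composite as a sensitivity analysis.
3. Use the same relatedness condition in both Table 1 headings, so that one column is the exact complement of the other. If two versions of the composite are kept, give each its own table.
4. Where related is used, say which relation counts. SAP 3.4 and 4.3 distinguish device alone from device and/or procedure, and 4.1 does not choose.

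The cost is SAP wording and one extra derived variable. Seriousness, severity and relatedness are already planned variables, so no new data are needed. The any-event success rate may be somewhat lower than the related-only rate.

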#### 4.3 Safety endpoints:

Type, seriousness, severity (as intensity), relatedness (device alone; device and/or procedure), Clavien-Dindo classification, SOC, High level term according to MedDRA, revisions and treatments needed and localization of pain concerning side effects occurred since implantation.

## **5. DISPOSITION OF SUBJECTS:**

The eligible population will include all patients who gave their informed consent and met the eligibility criteria. Patients who withdraw study before procedure (screening failure) won't be included in this population, as well as those who don't respect the inclusion criteria.

The ITT population will include all patients for whom a procedure has been performed even if the Altis sling has not been implanted (i.e Altis implantation failure and implantation of other device or none) among the eligible population excluding major deviation (GCP compliance), patient with no information at baseline, or patients implanted but not procedure form in eCRF.

All analyses will be performed on this population.

Last procedure happened in September 2020. As extraction of data is planned in July 2022, a few patients (20 approximatively) won't be able to complete the follow-up and/or the self-questionnaires at 3 years. Nevertheless, they should have theoretically completed their questionnaire at one year corresponding to the primary outcome; the data not completed at three years will be coded in a specific way to distinguish them to true missing values.

All visits for all patients included, whom data have been collected will be analyzed (baseline, first follow-up visit, 1 year, 2 years and 3 years after implantation). So, the final report will present longitudinal data and evolution over time of the different parameters (exams).

If any follow up visit is available, only patient's characteristics will be presented.

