## 2.2 Sample size:

Effectiveness of female SUIs managed with sling implantation is not accurately defined and large range of success of the procedure is reported.

Furthermore, definition of success is not standardized and comparison across studies and systems is not feasible due to different used endpoint criteria.

Accordingly if  $p$  is the % of success as defined in this protocol, the product  $p*(1-p)$  should be maximized. According to the interim results of an US study, the PGI score at 1 year is 89.3 %.

So this hypothesis of a 89 % rate could be chosen. Therefore, the minimal sample size to be included to detect this prevalence with a 5 % precision is given as following:

$$n = z^2 p(1-p) / d^2.$$

Precision ( $d$ ) = 5 %      prevalence ( $p$ ) = 89 %      estimated sample size  $n = 150$

The total number of subjects enrolled is not limited. However, a minimum of 150 subjects with 12-month available data will be collected. Taking into account a global attrition rate of 20%, 180 patients are targeted for enrolment.

When 150 subjects will have reached a minimal 12-month follow-up duration and all cases are judged exploitable, Sponsor will take the decision to stop or to continue the current recruitment.

Consequently, the centers have been encouraged to keep on enrolling patients after the first 180 patients defining an open-ended recruitment. Approximately 600 patients have been finally included.

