## 2.4 Study population:

This project involved 4 countries: France, Germany, Italy and Spain and surgeons used Altis in their current practice. Experience in Altis implantation may vary between investigators sites.

The study population will consist of patients meeting all of the inclusion criteria and none of the exclusion criteria.

Inclusion criteria are the following:

- Female gender
- At least 18 years of age
- Subject implanted with Altis Single Incision Sling System in the participating center, to manage urinary incontinence according to urologist's diagnosis
- Subject's having received written and oral information about study objectives and having accepted that anonymous data issued from his medical dossier will be used for research purposes and will be analyzed by using computer systems. According to national regulations, a written consent to participate may be required.

Exclusion criteria are the following:

- Subject who refuses to be included in the survey or that their medical data will be used for research purposes
- Indication for Altis Single Incision Sling System implantation is not for the treatment of female UI.
- Subject already enrolled in any investigational clinical trial of any treatment (drug or device).

Subject withdrawal:

Patients will be totally free to withdraw from the study at any time.

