## 2.6 Study product:

Altis Single Incision Sling (SIS) System is a CE-marked since 2012 and already marketed implantable device. All the patients included in this study had a surgery but a few of them have not been finally implanted with Altis (implantation failure) and another device may have been implanted (results from interim analysis).

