○ *Incision healing* (first post-operative visit only)

○ *Local pain* (first post-operative visit only)

○ *Physical examination / interview patient:*

- Weight, BMI and change of BMI since baseline (excepted at first post-operative

- visit)
  - Urinary symptoms
  - Nb of pads used (question from the investigator to the patient).
  - Cough stress test
- Pad weight test (if done, according to current practice)
- *PVR and uroflowmetry (if available):*
  - post-void residual volume measurement
  - maximum urinary flow rate
- New Vaginal/Pelvic Intervention (confirmed by the investigator), excepted at first post-operative visit
- Questionnaire PGI-I
- Questionnaire ICIQ –Ui-SF
  - Sum items 3+4+5
  - Items 6
- Questionnaire I-QOL:
  - total scores and subscale scores
- Questionnaire PISQ -12:
  - total scores
  - Q5, Q6 and Q7
- Work stoppage: if yes, number of days (first follow-up visit only).
- Normal activity: number of days before returning to a normal activity (first follow-up visit only).
- Patient satisfaction
- Patient recommendation: recommend the surgery to a friend?

ICIQ-UI Short Form scoring: The ICIQ-UI Short Form is a questionnaire for evaluating the frequency, severity and impact on quality of life (QoL) of urinary incontinence in men and women in research and clinical practice across the world. Questions 3, 4 and 5 are summed to compute the total ICIQ SF score. This score may be divided into the following four severity categories: slight (1-5), moderate (6-12), severe (13-18) and very severe (19-21).

i-QOL scoring: The I-QOL produces quality-of-life profiles for people suffering from urinary incontinence. The survey consists of 22 items scored on a 5-point Likert scale providing a transformed summary score of 0 to 100 with higher scores indicating better quality of life. The 22 items can be further grouped into 3 subscales: Avoidance and Limiting Behavior (8 items), Psychosocial Impacts (9 items), and Social Embarrassment (5 items). The I-QOL and its subscale scores are computed by adding each item's response, subtracting the lowest possible score and dividing that sum by the possible raw score range. The scores are then transformed to have a range from 0 (maximum problem) to 100 (no problem at all). The formula used to compute the transformed score follows:

Scale score = (sum of items - lowest possible score) / possible raw score range \* 100

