## **8. CHARACTERISTICS OF STATISTICAL ANALYSES:**

Descriptive statistics for continuous variables will be presented with  $N$ , *Mean*, *SD (standard deviation)*, *Median*, *Q1-Q3 (first and third quartile)*, where  $N$  denotes the number of subjects contributing with non-missing data.

For discrete variables, descriptive statistics will be presented with  $N$  and *percentage* of the number of subjects contributing with non-missing data in the various categories of the variable; the number of missing data will be presented but will not be taken into account in the percentage.

All statistical tests will be carried out as two-sided on a 5% level of significance. All confidence intervals will be 95% intervals.

Comparison between pre and post-operative endpoints for paired proportions will be done by a McNemar's test for binary variables.

Comparison between pre and post-operative endpoints for continuous variables will be done by a paired t-test if they are normally distributed. In case of absence of normality, the alternative is to use Wilcoxon's signed-rank test.

For both continuous or binary variables, the null hypothesis is "no difference between pre and post implantation" against the general alternative of "difference between pre and post implantation".

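### The single analysis set contradicts the Altis-implanted inclusion criterion, lets women given another device count as Altis successes, and drops some implanted women from the safety analysis

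*SAP*

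**What the plan says.** SAP section 5 builds its analysis set in two steps. The eligible population is consenting women who meet the eligibility criteria; those who fail an inclusion criterion are left out. The ITT population is then taken from within that group: "The ITT population will include all patients for whom a procedure has been performed even if the Altis sling has not been implanted". Major GCP deviations are removed from it, and so is any "patient with no information at baseline, or patients implanted but not procedure form in eCRF". Section 5 assigns all analyses to this set.

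SAP section 2.4, like the protocol synopsis, has as an inclusion criterion: "Subject implanted with Altis Single Incision Sling System in the participating center". SAP section 2.6 reports from the interim analysis that "a few of them have not been finally implanted with Altis (implantation failure) and another device may have been implanted".

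Success (SAP sections 4.1 and 9.2) has two parts: the PGI-I rating, and the absence of a serious or severe related adverse event. The Scientific Committee version uses a stricter PGI-I cut and adds related events of Clavien-Dindo grade 3 or higher. Neither version refers to whether Altis was implanted or whether the woman was later re-treated.

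Section 3.3 collects "New Vaginal/Pelvic Intervention (confirmed by the investigator), excepted at first post-operative visit", and sections 4.3 and 9.3 tabulate revisions. Section 9.3 counts incidence from the operative procedure to the last available follow-up. Section 5 ends by saying that for some women "only patient's characteristics will be presented"; as printed, the condition is that any follow-up visit is available, which presumably should read none.

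**The concern.** The primary objective is the effectiveness of Altis at one year, and monitoring its safety is part of the protocol's main objective. Three features of the single set work against this.

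- **The denominator is ambiguous.** One programmer could apply the inclusion criterion and drop implantation failures; another could follow the even-if clause and keep them. Each would be following the text.
- **Other treatments can be credited to Altis.** A woman whose Altis placement failed, who received another device and who rates herself much better meets the success definition. Her follow-up also enters the person-years for Altis complications.
- **Known implanted women leave the safety tables because a form is missing.** There is no separate safety population to catch them. The protocol synopsis asks sites to document all enrolled women, including those whose sling was revised early, so this exclusion runs against the study's own aim. Missing forms need not be unrelated to outcome.

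**Working it through.** **1. The two rules side by side.** Eligible means that all inclusion criteria are met, which includes Altis implanted. ITT is a subset of eligible. A woman without Altis therefore cannot be in the ITT set, and read literally the even-if clause admits nobody. Section 2.6 shows that such women exist, so the conflict affects real records.

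**2. The plan's own figure.** SAP section 2.2 assumes 89% success ("So this hypothesis of a 89 % rate could be chosen") and a precision of 5 points; section 8 sets the confidence level ("All confidence intervals will be 95% intervals"), so z = 1.96.

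n = 1.96² × 0.89 × 0.11 / 0.05² = 150.4. The stated 150 is reproduced, and the population question does not affect it.

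**3. Range of the coding choice.** Assumptions: 480 evaluable women, from about 600 included (section 2.2) × (1 − 0.20), using the SAP's attrition rate; k women not implanted, with k = 5, 10 or 20 because no count is given; 89% of them reporting improvement. Moving them from success to failure changes the rate by 0.89 × k / 480:

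| k | Change (points) |
|---|---|
| 5 | 0.9 |
| 10 | 1.9 |
| 20 | 3.7 |

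The 95% half-width at 480 is 1.96 × √(0.89 × 0.11 / 480) = 2.8 points.

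**4. Inclusion versus exclusion, a different question.** If implanted women succeed at rate p and the k others at rate q, the pooled rate differs from the implanted-only rate by (k/480) × (q − p). Take p = 0.89.

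- q = 0.89: no difference for any k.
- q = 1: 5/480 × 0.11 = 0.1 points up for k = 5, and 20/480 × 0.11 = 0.5 points up for k = 20.
- q = 0: 0.9 points down for k = 5, and 3.7 points down for k = 20.

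**5. Person-years.** With equal follow-up, non-implanted women supply k/480 of the person-time: 5/480 = 1.0% to 20/480 = 4.2%. If none of them had a counted event, the incidence rate would be diluted by that relative amount.

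**6. Implanted women dropped from safety.** No count and no event risk are given, so both are assumed: 600 women, 3 to 12 dropped, 3% observed risk in the rest.

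- All dropped women had an event: (0.03 × 597 + 3)/600 = 3.5% for 3 dropped; (0.03 × 588 + 12)/600 = 4.9% for 12 dropped.
- None had an event: 17.91/600 and 17.64/600, so 3.0% and 2.9%.

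The first line is a worst case, not an estimate. The two together show that the direction is open, with more room for understatement than for overstatement.

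**The case against.** Keeping implantation failures is deliberate, disclosed and ordinary ITT practice in a naturalistic cohort, and the even-if clause makes the intent fairly clear. This stands: the inclusion is defensible. What is missing is agreement with the eligibility rule and an implanted-only analysis beside it.

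A reader might go further in several ways that the documents do not support.

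- **That the Altis success rate is biased upward.** The 0.9 to 3.7 points compare two ways of scoring the same women. Step 4 shows that including them may leave the rate unchanged or even lower it.
- **That re-treated women generally count as successes.** Many re-operations would already be failures, through a serious or severe related event or, in the committee version, Clavien-Dindo grade 3 or higher. What remains is re-treatment not recorded as such an event, for example for persistent incontinence, and its size is unknown. The intervention item is also listed among the variables for analysis; it is only absent from the success definition.
- **That intra-operative events are lost for women without follow-up.** This rests on a garbled sentence. Section 5 also says that all visits with collected data will be analysed, and section 9.3 tabulates intra-operative events. The text needs clarifying; a loss is not established.
- **That sections 5 and 6 contradict each other on deviations.** Section 5 qualifies the exclusion as GCP compliance, which may be a different category from the protocol violations that section 6 sets aside. The conflict is weak.
- **That the primary composite should be recoded.** It is protocol-defined, and an interim analysis has taken place. A new failure rule belongs in a sensitivity analysis.

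It is also fair to say that, without a procedure form, the procedure date may be missing, so person-time cannot always be computed.

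**Conclusion.** The point holds on the text in three respects: the analysis set conflicts with the inclusion criterion; a woman given another device can count as an Altis success and add person-years, with no implanted-only analysis; and implanted women without a procedure form or baseline information are removed from the safety analysis.

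The size is unknown. The SAP says only that a few women were not implanted and gives no count of excluded implanted women. Under the assumption of 5 to 20 among 480 evaluable women, the scoring choice spans 0.9 to 3.7 points, which exceeds the 2.8-point half-width only towards the upper end. The effect on complication rates is of unknown direction, plausibly downward, and no figure for it can be drawn from the documents. This should be fixed, but it does not by itself invalidate the main result.

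**What to change.** 1. Define the eligible set as consenting women in whom an Altis procedure was attempted, so that it agrees with the even-if clause.
2. Keep the protocol and Scientific Committee composites as defined. Add (a) an analysis restricted to women implanted with Altis, and (b) a sensitivity analysis that counts as failure any implantation failure, and any new anti-incontinence procedure or sling removal before the visit. The new-intervention and revision data already collected serve for this.
3. Define a separate safety set: all consenting women with an attempted Altis procedure, regardless of baseline data, procedure form or follow-up. Tabulate their events, including intra-operative ones, report how many lack a procedure form, and compute person-time where a procedure date is available.
4. Reword the last sentence of section 5 so that women with no follow-up visit still contribute their intra-operative events, as section 9.3 implies.

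The cost is SAP wording and a few extra tables, with no new visits. The added analyses may show a slightly lower success rate or a higher complication rate.
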